- Once the woman is enrolled in the study a line will be added to the Antenatal Supplemental Visit Form stipulating the patient's participation in the study and the coordinator's phone number: Ex: "[name] study patient – page at admission ####-#####\*\*." This Form is a section of the EMR that is updated at each visit by the clinic provider with important/current antenatal issues; it is standard that the contraceptive plan for each patient is recorded here.

*Identification of study patients on L&D*

- The PCP on L&D may identify study patients who self-identify as being in the study. They will also be alerted by the "Study Patient" in the antepartum record if the patient has been enrolled antepartum. They will notify the research coordinator who will carry a phone during working hours.
- A reproductive health on-call fellow/attending will be designated 24-7 to ensure randomization and implant insertion within 24 hours for those randomized to the immediate group. After hours (nights and weekends), the research cell will forward to the reproductive health on-call fellow or attending. In addition, the voice message for the research cell will direct callers to contact the reproductive health on-call fellow through Amion, the hospital online paging system. A calendar will specify which co-investigator is on call for study patients.
- The PCP on L&D will call the research coordinator/call physician by phone or by text message that a study patient arrived on L&D for her birth.
- The research coordinator will review the list of admitted patients to L&D twice a day (8 AM and 4 PM) and once daily on Mother Baby Unit and Ob-Special care (Ob-Gyn wards) to identify enrolled study patients. This modality has been used with other studies in the department of Ob-Gyn and has been successful.

*Randomization*

- University of Utah coordinators will have access to UNM's REDCap to obtain randomization and enter any data collected for their participants.
- The research coordinator will access REDCap to obtain the randomization assignment for study patients (enrolled antepartum or on L&D not in labor) shortly after admission to L&D for a birth. The reproductive health physician on call will be notified

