- For patients enrolled postpartum, the research coordinator will randomize the patient as soon after consent is signed or verbally agreed to and within 22 hours after birth to ensure implant placement for those randomized to the immediate group within 24 hours. For those who verbally agree, we will make an effort to obtain written consent via mail, e-mail, or eConsent in the UNM HSC REDCap system.
- The reproductive health physician on call will be notified to ensure placement of the implant within 24 hours; after hours, the reproductive health physician on call will also have access to the randomization sequence and will notify the research coordinator of the subject's identification number.

**PROTOCOL TITLE: Effect of immediate versus standard postpartum insertion of the contraceptive implant on breastfeeding outcomes**

*Implant insertion*

- The implant will be placed in accordance with the Federal Drug Administration (FDA) label instructions and only by providers who have completed the Merck training and are certified to insert the implant by Merck.
- Those allocated to the immediate group will obtain their implant in the hospital, by residents with attending supervision, fellows, attendings or certified nurse-midwives, and by obtaining the implant through the hospital pharmacy or the implants from the Family Medicine grant or LARC Mentoring Program for UNM participants.
- For those randomized to the standard insertion group, the implant will be provided in clinics as per clinic protocol. For UNM participants without insurance or those whose insurance does not cover immediate implant insertion, a limited number of implants (33) will be provided through the Family Medicine grant and additional implants will be available via the LARC Mentoring Program. UNM and University of Utah have established a process to enter all clinical study data via REDCap.

*Follow-up procedures:*

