The questionnaires will contain data about breastfeeding, postpartum depression, and sexual function. A paper diary will be provided to aid the participant in daily recording of data. We will also include a retrospective data collection instrument to account for those we miss at the primary data collection points for breastfeeding information. If the primary questions have been answered either prospectively or retrospectively, then they get the normal prospective survey. If participants do not meet this criteria or if they miss a previous survey, then they will receive a retrospective survey. The diary will be collected at 2, 4, and 8 weeks. If possible, 2-3 good phone numbers will be obtained as well as addresses for each participant. Participants will have a phone number to contact study personnel at their specified site during standard work hours: Monday-Friday 8am- 4:30 pm with any concerns or adverse events. If they call after-hours, a voicemail system will be available, and the participant will be contacted the next working day.

*Data collection instruments*

Data collection instrument	Manner of collection	Timing	Included data
Enrollment form	Medical chart review  In-person, telephone and/or online via UNM's REDCap	After delivery  At enrollment	Participant & neonate medical history, delivery details  contraceptive history, contraceptive bridge-methods, lactation history, lactation and work expectations
Contraceptive Counseling Survey	In-person, telephone and/or online via UNM's REDCap	At enrollment and 4 weeks postpartum	Satisfaction with contraceptive counseling
Breastfeeding Survey	In-person, telephone and/or online via UNM's REDCap	2, 4, 8, 12, 24 weeks postpartum	Breastfeeding continuation, exclusivity, reasons for discontinuation if applicable, infant weight, resumption of intercourse, and satisfaction with contraception
EPDS	In-person, telephone and/or online via UNM's REDCap	2, 4, 8 weeks postpartum	Postpartum depression scale
FSFI	In-person, telephone and/or online via UNM's REDCap	4, 8, 12 weeks postpartum	Sexual function scale

PROTOCOL TITLE: Effect of immediate versus standard postpartum insertion of the contraceptive implant on breastfeeding outcomes

Bleeding diary	Paper or UNM's REDCap	Reviewed at 2, 4, 8 weeks. Collected at 2, 4, and 8 weeks	Bleeding patterns Side effects

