## **14. Provisions to Monitor the Data to Ensure the Safety of Subjects**

A Data and Safety Monitoring Plan has been developed and will be led by [name] at the University of New Mexico, who is an independent physician. [name] will monitor the study at least quarterly.

The ENG implant is an FDA approved drug, which has a well-established record in breast feeding women. Early implant insertion reflects standard practice in many centers, including the University of New Mexico. The data monitored and reviewed will include enrollment and dropout rates, protocol deviations, review of subject symptoms, and preliminary analysis of the primary outcomes (continuation of breastfeeding at 8 weeks). The reports will include enrollment and dropout rates, protocol deviations, review of subject symptoms, and preliminary analysis of the primary outcomes. The trial will be stopped for a cessation of breastfeeding in more than 70% of the early insertion group in the first 8 weeks. Any additional reports to the IRB will occur in response to specific events adverse events. Any serious adverse event defined as an event requiring re-hospitalization will require re-evaluation of the risk determination and continuation of the study. Adverse event reporting will follow

**PROTOCOL TITLE:** Effect of immediate versus standard postpartum insertion of the contraceptive implant on breastfeeding outcomes

guidelines as proposed by Good Clinical Practice and collected as they occur or are reported by patients. These reports will be compiled for review by the DSMB quarterly; except for serious adverse events which will be reported to the IRB and DSMB within 24 hours of the occurrence. All subjects will have access to clinical care which is not dependent on study participation and will be notified of the availability of that care. All data will be collected for quarterly reporting to the DSMB as well as for final data analysis and reporting. There may be times when we are required by law to share information. However, protected health information (PHI) will not be used in any published reports about this study.

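### Section 14's only written SAE definition is re-hospitalization: it omits serious events in the delivery stay, conflicts with the section's GCP reference, and carries a 24-hour clock that cannot always be assured

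*Combined protocol and SAP*

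**What the plan says.** Section 14 gives the definition and its first consequence in one sentence: "Any serious adverse event defined as an event requiring re-hospitalization will require re-evaluation of the risk determination and continuation of the study". The second consequence is timing. Adverse event reports in general go to periodic review: "These reports will be compiled for review by the DSMB quarterly". Events classed as serious are the stated exception and follow a faster route: "except for serious adverse events which will be reported to the IRB and DSMB within 24 hours of the occurrence".

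Two other sentences in Section 14 bear on scope. Adverse event reporting is to follow "guidelines as proposed by Good Clinical Practice and collected as they occur or are reported by patients". Separately, "Any additional reports to the IRB will occur in response to specific events adverse events". Neither lists criteria or sets a time limit.

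On where the exposure happens, Section 12.2 (Implant insertion) says: "Those allocated to the immediate group will obtain their implant in the hospital". Section 8.2 places standard insertions in the affiliated clinics, and Section 3.1 times them at 4-6 weeks.

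On how events reach the study, Section 12.2 (Follow-up procedures) schedules contacts at 2, 4, 8, 12 and 24 weeks. It gives participants a number staffed Monday to Friday, 8 am to 4:30 pm: "If they call after-hours, a voicemail system will be available, and the participant will be contacted the next working day". Section 12.2 (Identification of study patients on L&D) describes separate cover: "A reproductive health on-call fellow/attending will be designated 24-7 to ensure randomization and implant insertion within 24 hours". The research cell is forwarded to that physician on nights and weekends.

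**The concern.** A woman who has not yet gone home cannot be re-hospitalized. If the written definition is applied as it stands, a death, a life-threatening event or a prolonged stay between immediate insertion and discharge triggers neither the 24-hour report nor the re-evaluation of the study. It joins the quarterly compilation. The hours after in-hospital insertion are the exposure this trial adds to usual timing, so this is where expedited review matters most. After discharge, a lasting nerve injury or an extensive removal procedure (both among the risks in Section 18.1) would also fall outside if no admission followed.

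The definition also treats insertion events differently by arm, because one arm has the implant placed before discharge and the other after it. Finally, a clock that starts at occurrence assumes that the team learns of events almost at once, and the contact arrangements do not provide for that in every case.

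**Working it through.** The plan gives no figure to reproduce. The check compares the sentences with each other and then measures the elapsed times that the contact arrangements allow.

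**1. What the definition captures.** Inputs: the definition in Section 14 and the insertion settings in Sections 8.2 and 12.2. Read literally:

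| Serious event | Immediate arm | Standard arm |
|---|---|---|
| Insertion event during the delivery stay that prolongs it | Not an SAE | Cannot arise (no implant yet) |
| Insertion event after discharge leading to admission | SAE | SAE |
| Insertion event after discharge, lasting harm, no admission | Not an SAE | Not an SAE |
| Obstetric event during the delivery stay | Not an SAE | Not an SAE |

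The arms differ only in the first row. A complication at insertion that needs inpatient care appears there as a longer stay in the immediate arm and as an admission, which counts, in the standard arm. The other omissions apply to both arms.

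**2. Who is exposed to the gap.** Section 5.3 aims for 75 women per group and allows up to 200 in total. With equal allocation, 200 / 2 = 100 per group. So 75 to 100 immediate-arm women pass through the uncovered interval. This counts women, not missed events; the documents give no rate of serious in-stay insertion events.

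**3. Delay if an event is handled as non-serious.** Quarterly review: 52 / 4 = 13 weeks at most, against 24 hours.

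**4. Delay through the participant telephone line.** Staffed hours are Monday to Friday, 08:00 to 16:30. Times run from voicemail to the next opening:
- Weeknight, 16:30 to 08:00: 7.5 + 8 = 15.5 h, inside 24 h.
- Weekend, Friday 16:30 to Monday 08:00: 7.5 + 24 + 24 + 8 = 63.5 h, outside 24 h.
- Voicemails that wait more than 24 h for the next opening are those left between Friday 16:30 and Sunday 08:00: 7.5 + 24 + 8 = 39.5 h. As a share of the week, 39.5 / 168 = 23.5%, before holidays.

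These figures assume a call-back at opening time. They start at the voicemail, whereas the protocol's clock starts earlier, at the event.

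**5. Delay if the event is not volunteered.** Gaps between successive contacts (birth, then weeks 2, 4, 8, 12, 24) are 2, 2, 4, 4 and 12 weeks, that is 14, 14, 28, 28 and 84 days. An event just after the week-12 contact could first be learned of 12 weeks later.

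**6. When the clock can be met.** Events seen by staff during the delivery stay, or phoned in promptly on a working day, can be reported within 24 hours of occurrence.

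**The case against.** The strongest reply is that Section 14 should be read as a whole. It says reporting will follow GCP and that further IRB reports will respond to specific adverse events, so an investigator could well report an in-stay death at once. This stands in part: the section is inconsistent rather than clearly exclusionary, and one cannot say that such events would certainly escape expedited review. It does not close the gap. Those sentences give no criteria and no deadline, while the only explicit definition is the narrow one, and two sites under two IRBs (Section 11.1) could resolve the conflict differently.

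A reader might infer that SAE comparisons will favour immediate insertion. The documents do not support that. Neither the endpoints in Section 7 nor the analyses in Section 13 include a by-arm SAE comparison, and in-stay obstetric events are omitted in both arms. What remains is unequal capture of insertion-related events, which matters for monitoring and for any table of SAEs.

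A reader might also infer that the 24-hour limit is impossible to meet or will routinely be missed. Step 6 shows that it can be met for some events, a weeknight voicemail waits only 15.5 h, and no event frequency is given that would support routine breach.

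Three further points narrow the concern. Suicidal ideation has its own pathway in Section 18.1, with contact as soon as possible or the same day, so it is not a good example of neglect, although that pathway does not mention IRB or DSMB reporting. Section 11.2 provides bi-monthly, possibly monthly, contact between sites that covers adverse events; this may bring news sooner but is not IRB or DSMB review. Section 15.2 ends data collection when an implant is removed, so a wider definition alone would not secure follow-up of removal complications.

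Nor can one conclude that participants' after-hours calls never reach a physician. One part of Section 12.2 forwards the research cell to the on-call physician, another sends participants' calls to voicemail, and the text does not say whether these are the same line.

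**Conclusion.** The point holds as an internal inconsistency with a safety consequence. The only written SAE definition is re-hospitalization, and it governs both the re-evaluation of the study and the 24-hour report. Taken literally, it moves serious events without readmission, including those in the hours after immediate insertion, from a 24-hour report to a review up to about 13 weeks away. Capture of insertion-related events that need inpatient care differs between arms. The clock from occurrence cannot be assured for voicemails left in 23.5% of the week (longest wait 63.5 h, before holidays) or for events first learned at contacts up to 12 weeks apart.

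This rests on two assumptions. The first is that staff would apply the explicit definition where it differs from the general GCP sentence; the documents do not say which prevails. The second is that the GCP criteria are wider than readmission; the document refers to ICH-GCP E6 but does not reproduce its list. The number of events affected cannot be estimated from the documents. The primary endpoint, margin and primary analysis are not affected.

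**What to change.** In Section 14:
- Replace the re-hospitalization definition with the GCP seriousness criteria that the section already invokes, written out in full, and state expressly that events during the delivery stay are covered, including its prolongation.
- Count SAEs from randomization in both arms and tabulate them by arm.
- Start the 24-hour clock when the study team becomes aware of the event.

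In Section 12.2, reconcile the on-call forwarding with the after-hours voicemail, so that it is clear where a participant's after-hours adverse event call goes.

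The cost is protocol wording, one added form field and a few more expedited reports. Some of these will concern obstetric events unrelated to the implant, in either arm; the by-arm tabulation puts them in context.

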## **15. Withdrawal of Subjects**

- 15.1 The research team will provide thorough screening to see if the patient will meet inclusion and exclusion criteria. If any circumstances arise such participant experiencing exclusion criteria during study participation or fail to follow study procedures such as having the implant placed or removed before the study ends, the participant will be notified and withdrawn from the study without their consent.
- 15.2 Participants may have their implant removed at their request at any time. However, removal of the implant automatically terminates participation in the study and no data will be collected further. The data that was already collected from those participants that withdraws or was withdrawn from the study will be used for data analysis.
- 15.3 NA
- 15.4 Participants may withdraw from study involvement at any point in time and this will not affect their ability to obtain standard clinical care that day. All data points will be collected on the date of the procedure and therefore we anticipate loss to follow up and withdrawal rates will be low. Participants will be given the information on how to withdraw in the study consent.
- 15.5 The authorization for the use and disclosure of the participant health information for this study shall not expire unless the participant cancels this authorization. The health information will be used or disclosed as long as it is needed for this study. However, the participant may withdraw her authorization at any time providing a notification to the UNM investigators in writing to notifying the study team about the withdrawal. To do this, a letter should be sent to:

[name]  
Department of Obstetrics and Gynecology  
[name]  
[name]

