#### **4. Inclusion and Exclusion Criteria**

4.1. Potential participants may be identified in the following locations/timeframes: 1) antenatal clinics, 2) visits to OB-Triage 2) on admission to L&D for delivery not in active labor or 4) during the first postpartum hours in the Ob-Gyn ward of the UNM Hospital and University of Utah Hospital.

- When women decide on an implant as a postpartum contraceptive in any of these venues, the PCP (Ob-Gyn, Family Medicine physicians/residents and midwives) may discuss the patient's interest in hearing about the study and may contact the research coordinator by a message in the EMR or by phone or in person to let her know that the patient is interested in hearing about the study.
- Additionally, the research coordinator will review antenatal clinic, OB Triage and inpatient (L&D and postpartum) lists to assess patients' contraceptive plan through review of the EMR.
- If the patient expresses interest, the research coordinator and/or a study co-investigator will explain the study, screen the patient for eligibility and obtain informed consent.
  - *Note: Hepatitis C will not be considered an exclusion criterion. Mothers with Hepatitis C can breastfeed per the Centers for Disease Control and Prevention. However, HCV is spread by infected blood. Therefore, if the HCV-positive mothers' nipples and/or surrounding areola are cracked and bleeding, she should stop nursing temporarily. To maintain her milk supply while not breastfeeding, she can express and discard her breast milk until her nipples are healed. Once her nipples are no longer cracked or bleeding, the HCV-positive mother may fully resume breastfeeding. If we identify a mother with hepatitis C, we will assess through follow up questionnaires when they stopped breastfeeding, if they continued to express milk during the period of no lactation and when they restarted lactation.*
  - *Note: We will continue enrollment in the study for all women regardless of the infants' status; we will perform a secondary sub-group analysis of women/infants with complications in order to improve the ability to generalize from the study.*

We request a waiver of HIPAA for screening/recruitment purposes.

**PROTOCOL TITLE: Effect of immediate versus standard postpartum insertion of the contraceptive implant on breastfeeding outcomes**

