**Exclusion Criteria**

- Under age 13
- History of breast cancer (screen by past medical history)
- History of undiagnosed vaginal bleeding (screen by past medical history)
- Head trauma that affected pituitary function (screen by past medical history)
- Prolactin insufficiency (screen by past medical history)
- Previous lactation failure (defined as no lactation within 5 days postpartum)
- Any contraindication to lactation/implant use including diseases transmittable by breast milk (screen by past medical history)
- Liver dysfunction (screen by past medical history)
- Use of drugs that inhibit lactation (screen by medical history)
- Sensitivity to the components of the ENG implant (screen by past medical history)
- Contraindications to use the implant by the (US MEC) (screen by past medical history)
- Active labor
- Delivery at  $<$  37 weeks gestational age

There is a description of different inclusion/exclusion criteria between the sites. UNM Is recruiting minors under age 18 and over the age of 13, and the University of Utah is not recruiting minors. This is the only difference in the protocols.

4.3. This study will include pregnant adolescent and adult women. This study will not recruit adults who are unable to consent or women who are incarcerated.

4.4. This study will recruit women who can speak and read English and/or Spanish fluently.

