## **20. Recruitment Methods**

20.1. (Also described under “procedures” in Section 12.) Patients may be recruited in the following locations/timeframes: 1) antenatal clinics, 2) visits to OB-Triage 2) on admission to L&D for delivery not in active labor or 4) during the first postpartum hours in the Ob-Gyn ward of the UNM Hospital and University of Utah Hospital.

- Patients may be asked for their contraceptive choice in any of these four venues, although ideally in antenatal clinics during prenatal care. When women decide on an implant as a postpartum contraceptive in any of these venues, the PCP (Ob-Gyn, Family Medicine physicians/residents and midwives) may discuss the patient’s interest in hearing about the study and may contact the research coordinator by a message in the EMR or by phone or in person to let her know that the patient is interested in hearing about the study.
- Additionally, the research coordinator will review antenatal clinic, OB Triage and inpatient (L&D and postpartum) lists to assess patients’ contraceptive plan through review of the EMR. The research coordinator may contact patients who have decided on a postpartum implant to assess her interest in participating in the study.
- If the patient expresses interest, the research coordinator will present the study and ask the patient for her interest in enrolling. If interested, the research coordinator and/or a study co-investigator will explain the study, screen the patient for eligibility and obtain informed written or electronically signed consent.
- Women will not be approached for study participation if they are in active labor. Women will be approached and enrolled, if interested, either prior to active labor (e.g., when admitted for induction of labor or scheduled cesarean delivery) or after delivery.
- We will not enroll patients who are under sedation. Most participants will be enrolled and undergo informed consent in the antenatal period; some will be

**PROTOCOL TITLE:** Effect of immediate versus standard postpartum insertion of the contraceptive implant on breastfeeding outcomes

enrolled when they are admitted to labor and delivery not in active labor; neither of these two groups would be under sedation. For those “up to 22 hours after delivery,” we will only enroll women who have not received sedation within a 4-hour period.

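### Section 15.1 withdraws women who meet an exclusion criterion after randomisation, some for reasons tied to the primary failure event, and the plan does not say how their 8-week outcome is obtained or counted

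*Combined protocol and SAP*

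**What the plan says.** Section 15.1 lists grounds on which the team ends participation. One is a "participant experiencing exclusion criteria during study participation"; the consequence is that "the participant will be notified and withdrawn from the study without their consent". The wording does not separate the time before randomisation from the time after it.

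The criteria are those under Exclusion Criteria in Section 4.2. Two bear directly on lactation: "Use of drugs that inhibit lactation (screen by medical history)" and "Any contraindication to lactation/implant use including diseases transmittable by breast milk (screen by past medical history)".

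The primary endpoint (Sections 3.1 and 7.1) is any breastfeeding at eight weeks; Section 13.2 frames failure as having stopped by then. Section 13.1 makes the per-protocol analysis primary and intention to treat (ITT) secondary, and defines neither set.

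On data after withdrawal, Section 15.2 says: "The data that was already collected from those participants that withdraws or was withdrawn from the study will be used for data analysis". The explicit stop to data collection is attached to a different event: "removal of the implant automatically terminates participation in the study and no data will be collected further". The instruments table in Section 12 provides a chart review of breastfeeding up to one year, for use when a survey is not answered.

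**The concern.** Starting a lactation-inhibiting drug or acquiring a contraindication to lactation after randomisation is closely linked to stopping breastfeeding. Withdrawal on those grounds therefore depends on the outcome. If the woman leaves before her cessation is recorded, the plan gives no route to her 8-week status and no rule for classifying her. In the per-protocol primary analysis she would probably drop out of both numerator and denominator.

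In a non-inferiority trial, losing failures from the test arm moves the estimate towards the claim. The protocol's own rationale in Section 2.1 is that early progestin could in theory impair lactogenesis, so arm-related loss cannot be dismissed. No blinding is described, so staff deciding whether a criterion has been met would know the allocation. The endpoint is also a safety endpoint (Section 7.2), and the Section 14 stopping rule uses the cessation rate in the early group, so lost failures would also weaken monitoring.

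**Working it through.** **Inputs from the plan (Sections 5.3 and 13.2).** Standard-arm discontinuation 30%; margin 15 percentage points; one-sided 5%; unpooled Z test; 62 evaluable women per arm.

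**The plan's own figure.** With 30% in both arms, n per arm = 2 × 0.30 × 0.70 × [(1.645 + 0.842)/0.15]² = 115.4, so 116 rather than 62. With 62 per arm, power is about 57%. That is a separate matter. Here 62 is used only as the plan's stated evaluable size.

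**Assumptions.** The documents give no rate for these withdrawals. I take k = 2, 4 or 6 immediate-arm failures lost, and vary what happens in the standard arm. True discontinuation is set at the margin, 45% immediate against 30% standard, where a non-inferiority claim is false and should occur 5% of the time. Expected failures are 0.45 × 62 = 27.9 and 0.30 × 62 = 18.6.

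**Formulas.** A lost failure leaves numerator and denominator:

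- p_I = (27.9 − k)/(62 − k)
- p_S = (18.6 − j)/(62 − j), where j is the number lost from the standard arm
- d = p_I − p_S
- SE = √[p_I(1 − p_I)/(62 − k) + p_S(1 − p_S)/(62 − j)]
- P(claim) = Φ[(0.15 − d)/SE − 1.645]

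**Worked case, k = 4, j = 0.** p_I = 23.9/58 = 41.2%; p_S = 30%; d = 11.2 points; SE = 0.087. P = Φ[(0.150 − 0.112)/0.087 − 1.645] = Φ(−1.21) = 11.3%.

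**Results.** The cells show the expected difference in points, then the false non-inferiority rate. With nothing removed they are 15.0 and 5.0%.

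| Immediate-arm failures lost (share of 27.9) | Immediate arm only (j = 0) | Same share from both arms (j = 18.6k/27.9) | Same count from both arms (j = k) |
|---|---|---|---|
| 2 (7%) | 13.2; 7.6% | 14.7; 5.4% | 15.5; 4.4% |
| 4 (14%) | 11.2; 11.3% | 14.3; 5.8% | 16.0; 3.9% |
| 6 (22%) | 9.1; 16.6% | 13.9; 6.4% | 16.6; 3.3% |

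The direction depends on the pattern. One-sided loss from the immediate arm inflates the error materially, a common share inflates it slightly, and equal counts make the test conservative.

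**Where the text leaves these women.**

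- A cessation reported before withdrawal is kept under Section 15.2 and can be counted.
- A woman withdrawn in the first week, before the 2-week survey, may have no feeding outcome on file.
- Chart review is tied to survey non-response. The plan does not say whether it applies to a woman who has been withdrawn and is no longer surveyed.
- ITT analysis needs an 8-week status or a rule for its absence, and neither is given.

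**The case against.** The strongest reply is that Section 15.1 does not say failures are discarded. Collected data are retained, an ITT analysis is planned, and chart review might recover some outcomes. Most listed criteria are worded as history screens at entry. Several, such as liver dysfunction or pituitary trauma, have no evident link to insertion timing and would be expected about equally in both arms. A woman who stops and only then takes a suppressing drug may already have reported stopping. Low milk supply is not itself a listed criterion. The larger error rates require one-sided loss, which at k = 6 means 22% of immediate-arm failures and none in the other arm.

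Much of this stands. It rules out saying that the plan removes failures instead of counting them; the text leaves the matter open. It also makes arm-differential loss a risk rather than an expectation. It does not supply the missing rule, because Section 15.1 expressly carries the criteria into study participation.

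Two stronger readings are tempting and unsupported. Since "Most participants will be enrolled and undergo informed consent in the antenatal period" and active labor is on the exclusion list, a reader might infer that the rule withdraws most of the trial. Sections 12.2 and 20.1 use active labor to limit when women may be approached and enrolled, and randomisation follows admission for birth, so that reading is strained. A reader might also see a conflict with the Section 4.1 note beginning "We will continue enrollment in the study for all women regardless of the". That note concerns the infant's status, whereas the Section 15.1 criteria concern the mother. The neighbouring hepatitis C note in fact shows an intention to follow women whose breastfeeding is interrupted.

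**Conclusion.** The concern holds in limited form. Section 15.1 forces post-randomisation withdrawal for reasons tied to the primary failure event. The plan neither secures the 8-week outcome of these women nor says how they are classified, and its primary analysis is per protocol.

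The effect on the false non-inferiority rate runs from a small reduction (3.3% at the lowest) through slight inflation (up to 6.4%) to material inflation (16.6%) across the assumed patterns. Only loss concentrated in the immediate arm gives the material inflation. Both the counts of 2 to 6 and the split between arms are assumptions, and the results apply to 62 per arm with a true difference exactly at the margin. The documents do not establish that such loss will occur or favour one arm. If the 8-week data are never collected, however, the analysis may be unable to recover them.

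**What to change.** In Section 15.1, state that the Section 4.2 exclusion criteria determine eligibility up to randomisation only. For a criterion that emerges after randomisation:

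- record it with its date, and do not end study follow-up because of it;
- keep collecting 8-week feeding status through the existing surveys or chart review where consent allows, and say that the chart review covers these women;
- in the ITT analysis, count actual status, with not breastfeeding at 8 weeks counted as discontinued;
- do not drop a woman from the per-protocol set solely because she met such a criterion after randomisation.

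Define both analysis sets in Section 13.1 and reconcile Sections 13.1, 15.1 and 15.2. Add a sensitivity analysis for any of these women whose 8-week status is still unknown, and report their number by arm.

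The cost is a short amendment using instruments already in place. The downside is a possibly higher observed discontinuation rate. The change concerns follow-up and analysis only; clinical care is unaffected.
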